Fortification of human milk is institution-specific and no standard of care has been recommended regarding the timing of fortification of human milk feeds in preterm infants. Much of the concern for earlier fortification arise over whether comorbidities, such as NEC and feeding intolerance, will be more prominent in infants provided early fortification versus delayed fortification. To date, no studies have demonstrated a relationship between human milk fortifiers and the incidence of NEC or feeding tolerance. Thus, delays in introducing HMF may represent an unwarranted safety concern that interferes with supplying an appropriate nutrient-enriched diet to preterm infants. For example, 34.3% of preterm infants are diagnosed with post-natal growth failure at the Children's Hospital of Georgia. Further, later introduction of HMFs may lead to longer time to reach full enteral feeds, total duration on total parenteral nutrition (TPN), or duration of central venous line use. Current available evidence suggests that fortification of human milk starting at the first feed is safe and well-tolerated and may have substantial benefit for preterm infant growth.

3. Inclusion and Exclusion Criteria

List the inclusion/exclusion criteria:

Inclusion:

1. Birth weight 1000-1500 grams
2. Admitted to AU NICU within 24 hours of life
3. Maternal intent to use human milk (maternal or donor milk)

Exclusion:

1. Congenital anomalies including congenital heart disease or other major defect requiring surgical intervention
2. Feeds not started within first 96 hours of life
3. Intrauterine growth restriction (IUGR) defined as <3rd % on a gender specific Fenton growth curve

4. Number of Subjects/Records/Samples Collected

Indicate the total number of subjects to be accrued/records reviewed/samples collected across all sites:

The sample size was determined assuming an alpha level of 0.05, power of 80%, a common standard deviation of 3.64, and a two-sided two-sample t-test to examine differences in weight growth velocity at 28days between the two feeding protocol groups. The mean for the standard of care group (fortification beginning on day 8) was 10.6% and for the intervention group (fortification beginning on day 1) was 12.3, 12.6 and 13.6. The sample size required for each mean difference is below

Assumed Mean in Each Group		Sample Size 2. per Group
Fortification Day 8	Fortification Day 1	
10.56	12.25	74
10.56	12.56	53
10.56	13.56	25

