4. Parenteral nutrition will be provided as outlined in the standard NICU feeding protocol and will be consistent with parenteral intake provided to all VLBW infants in the NICU regardless of study participation.
5. Enfamil HP HMF will be added to provide 22 calories/ounce on the initiation of enteral feeds for the intervention group (feeding day 1). For the control group, Enfamil HP HMF will be added to provide 22 calories/ounce when enteral feeding volume reaches 80 mL/kg/day (feeding day 8). Caloric density will be advanced to 24 calories/ounce at feeding day 10 for both groups. The caloric density progression follows the standard NICU fortification practices.

Blinding Procedures

Feeding tolerance is largely subjective. As an important secondary outcome, we will blind all healthcare personnel to study group allocation for the first 7 feeding days.

1. Upon consent, participants will be randomized to one of two study groups.
2. The milk bank in the NICU is responsible for all human milk preparation. Milk bank technicians will receive the group allocation for each participant and prepare human milk with/without fortification according to standard formulations.
3. Group allocation for each participant will be recorded by milk bank technicians on the daily feeding sheets (standard procedures for all infants). Group allocation and fortification will be confirmed by one study member of the study team who will be unblinded (co-Investigator [name] who is the NICU dietitian that oversees the milk laboratory).
4. Blinding will be accomplished by removing the caloric content from the label for all study participant. In the field that contains calories, “study participant” will be entered. Blinding will occur during the first 7 feeding days and calorie content will be recorded on feeding day 8 and all subsequent feeding days.

Intervention Group

	Parenteral Nutrition/IV Fluids				Enteral Feedings Given by 30-60 minute bolus q 3 hours NG/OG		Intervention Group
Feeding Day	Glucose mg/kg/min	Protein, g/kg	Lipids, g/kg	IVF, mL/kg	Enteral Feedings, mL/kg	Feeding Type	Notes
Day 1	6-10	3.5-4	3	80-130	20	Human Milk +HP HMF	Add Enfamil High Protein Human Milk Fortifier to 22 calories
Day 2	6-10	4	3	80-130	20	Human Milk +HP HMF	
Day 3	6-10	4	3	90-110	40	Human Milk +HP HMF	
Day 4	6-10	4	3	90-110	40	Human Milk +HP HMF	
Day 5	6-10	4	3	70-90	60	Human Milk +HP HMF	
Day 6	6-10	3-4	3	70-90	60	Human Milk +HP HMF	
Day 7	6-10	2.5-4	2	50-70	80	Human Milk +HP HMF	

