Briefly describe the actual source records or measures that will be used to collect data about participants. (All surveys, interview scripts, and data collection forms will be attached elsewhere in the application. Do not add other documents to the protocol.) Describe what data will be collected and how it will be collected at all measurement/data collection time-points.

Data will be collected from the patient's EMR. Data to be collected include: date of birth, gender, estimated gestation age (EGA), Apgar score at 1 and 5 minutes, weights, head circumference, length, z-scores for weight, length, and head circumference, total volume of feeds and TPN, number of missed enteral feeds, maternal milk vs donor milk volumes. Laboratory data including basic metabolic panel, magnesium, phosphorus, alkaline phosphatase and urine sodium, potassium and magnesium will be collected on day 22 as per the current standard of care. No blood collections or other procedures will be performed specifically for the study. Clinical outcomes will be collected to include: incidence of metabolic acidosis, NEC, oxygen requirement at 36 weeks, PDA, and death.

Anthropometrics

Anthropometrics are measured as part of the standard physical assessment of the preterm infant. For this study, all anthropometric measurements and calculations will follow AU's standard preterm infant physical assessment guidelines.

Weight

1. Body weight will be measured within 24 hours of birth and then every 7 days until 28 days of life and again at 36 weeks post-menstrual age (PMA).
2. Measurement of weight will be performed by the principal investigator (PI) and/or co-Investigators
3. Weight will be measured (x 2) on a tared infant scale calibrated to the nearest 10 grams. Weights will be recorded in grams (g). Discrepancies of greater than 20g will be repeated.
4. Infants will be weighed without a diaper.
5. Average weight will be recorded in the EMR and documented in the database.
6. Weight will be plotted on a gender-specific Fenton growth chart in the EMR and the percentile recorded in the database

Weight Gain

1. Weight gain and growth velocity (GV) will be calculated at 28 days of life and 36 weeks PMA.
2. Weight gain will be recorded as g/day
3. GV will be calculated as follows and recorded in the database:

$$GV \text{ (g/kg/day)} = \frac{[1000 \times (Wn - W1)]}{(Dn - D1) \times \left[\frac{Wn + W1}{2} \right]}$$

W= weight in grams

D = day

1 = interval of time chosen

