To examine differences between the two groups and assess for potential confounding variables two-sample t-tests will be used for continuous variables, chi-square tests will be used for categorical variables, and Wilcoxon Rank Sum tests will be used for ordinal data. Variables that will be examined include all collected EMR data (e.g., demographics, feeding related, laboratory, and clinical measures) and anthropometric measures.

To examine differences between the two groups (day 1 vs. day 8), a simple two-sided two-sample t-test will be used as a preliminary test for differences in continuous outcomes (e.g., weight growth velocity, head circumference growth velocity, length growth velocity, zscores). Then, to control for various potential confounders or covariates, analysis of covariance (ANCOVA) will be used with the main effect of interest being the group effect. Covariates that will be adjusted for include gestational age, total number of feed interruptions, incidence of metabolic acidosis, and NEC. Because there are only two groups, no adjustment to the overall alpha level will be needed to control for multiple comparisons.

b. When applicable, provide a power analysis:

N/A

The sample size was determined assuming an alpha level of 0.05, power of 80%, a common standard deviation of 3.64, and a two-sided two-sample t-test to examine differences in weight growth velocity at 28days between the two feeding protocol groups. The mean for the standard of care group (fortification beginning on day 8) was 10.6% and for the intervention group (fortification beginning on day 1) was 12.3, 12.6 and 13.6. The sample size required for each mean difference is below

Assumed Mean in Each Group		Sample Size per Group
Fortification Day 8	Fortification Day 1	
10.56	12.25	74
10.56	12.56	53
10.56	13.56	25

A sample size of 25 per group, for a total of 50 subjects will be needed.

c. Describe how data and specimens will be handled:
 
Data will be collected and recorded on a coded spreadsheet that is stored on a research specific Box drive assigned by AU IRB.
	 N/A

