
c. If applicable, describe procedures that will be followed when subjects withdraw from the research, including partial withdrawal from procedures with continued data collection.
	 N/A
--	---

12. Risks to Subjects

a. List the reasonably foreseeable risks.
 
 1. Physical risks: Minimal risk of feeding intolerance due to early fortification. Feeding intolerance may present as spit up, irritability, or abdominal distention. Possibility of increased risk of developing NEC, an intestinal infection. 2. Psychological risk: no psychological risk 3. Social risk: no social risk 4. Legal risk: no legal risk 5. Parents or legal guardians have no financial risks associated with this study. 6. There will be no financial costs associated with inclusion in this study 	 N/A

b. If applicable, describe any costs that subjects may be responsible for because of participation in the research.
	 N/A

13. Potential Benefits to Subjects

Describe the potential benefits that individual subjects may experience from taking part in the research.

Introducing higher caloric feeds at the onset of enteral feeds can improve growth outcomes for VLBW infants when compared to infants who begin fortification after the first week of life.

14. Confidentiality

Describe the procedures for maintenance of confidentiality.

1. Subjects are at risk of breach of confidentiality. All research team members have undergone confidentiality training (CITI, HIPAA, and PHI) and are aware of the consequences for breach of confidentiality.
2. To protect subject privacy, data folders in use during testing will not contain personal identifiers and forms containing personal identifiers will be kept out of public view.
3. All subjects will be given a unique identifier.
4. Research raw data will be stored on a drive that is password protected, and databases will be stored on the AU IT provided human research drive. Only the PI and the co-investigators will have access to the drive.
5. If an unanticipated research-related event arises, the PI will be immediately informed of the event. If the event requires medical attention, the study physicians will be contacted for decisions regarding further action as needed.

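### The ANCOVA adjusts for feed interruptions, metabolic acidosis and NEC, which follow randomisation, so its group effect need not be the total effect of early fortification on growth

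*Protocol*

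**What the plan says.** Section 9a sets out two analyses of the continuous outcomes, weight growth velocity among them. First, "a simple two-sided two-sample t-test will be used as a preliminary test for differences in continuous outcomes". Then, to control for potential confounders or covariates, "analysis of covariance (ANCOVA) will be used with the main effect of interest being the group effect". The covariates are listed: "Covariates that will be adjusted for include gestational age, total number of feed interruptions, incidence of metabolic acidosis, and NEC". Neither analysis is named as primary. The sample size (sections 4 and 9b) rests on the unadjusted two-sided t-test.

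On timing, section 8b (Blinding Procedures) says: "Upon consent, participants will be randomized to one of two study groups". The intervention group receives fortified milk from the first feed.

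On the status of the covariates:

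- Section 8 (Data Types and Source Records): "Clinical outcomes will be collected to include: incidence of metabolic acidosis, NEC, oxygen requirement at 36 weeks, PDA, and death".
- Section 8b treats feeding tolerance as an important secondary outcome and gives it as the reason for blinding staff.
- Section 12a lists "Minimal risk of feeding intolerance due to early fortification" and a possible increase in NEC among the foreseeable risks.
- Section 2 describes the general worry that "comorbidities, such as NEC and feeding intolerance, will be more prominent in infants provided early fortification versus delayed fortification", and also suggests that "later introduction of HMFs may lead to longer time to reach full enteral feeds".

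**The concern.** Section 1 asks whether early fortification improves growth at 28 days. That is a question about the total effect of being assigned to it, including whatever it does to growth through feeding tolerance or illness. Section 9a poses no direct-effect question.

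A variable that arises after assignment cannot confound a randomised comparison, but assignment can change it. Adjusting for it then removes the part of the effect that runs through it. Where the covariate and growth share an unmeasured cause, such as severity of illness, adjustment adds a further bias.

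The error can go either way. If fortification causes more interruptions or NEC and these slow growth, the adjusted estimate credits it with growth the infants did not have. If fortification reduces them, a real benefit is hidden. The t-test and the ANCOVA could then disagree, and the protocol has no rule on which one answers the question.

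**Working it through.** **1. The plan's own figure.** Inputs from sections 4 and 9b: SD 3.64, two-sided alpha 0.05, power 80%, control mean 10.56, intervention means 12.25, 12.56 and 13.56. The differences are 1.69, 2.00 and 3.00. A noncentral-t calculation gives 73.8, 52.97 and 24.1 per group, which round up to the stated 74, 53 and 25. At 25 per group and a difference of 3.0, power is 81.5%. The sample size is reproduced, for the unadjusted t-test.

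**2. Timing of each covariate.**

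| Covariate | Relation to randomisation |
|---|---|
| Gestational age | Before; a valid baseline covariate |
| Total feed interruptions | After; none can precede the first feed, when fortification starts |
| NEC | After; collected as an outcome |
| Metabolic acidosis | At least partly after; collected as an outcome, time window not defined |

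**3. Size of the bias, one covariate.** Let g be the group (0/1), T the total effect, a the shift of the covariate m caused by fortification (in SDs), and r the within-group correlation of m with growth velocity y.

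- m = a·g + N(0,1)
- y = 10.56 + (T − a·b)·g + b·m + e, with b = r × 3.64 and SD(e) = 3.64 × √(1 − r²)

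The within-group SD of y is then 3.64 and the t-test estimates T. The ANCOVA on g and m estimates T − a·b, so bias = −a × r × 3.64.

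The values of a and r below are assumptions; the protocol gives none.

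| Size of a | r | Size of bias (g/kg/day) | Share of 3.0 |
|---|---|---|---|
| 0 | any | 0 | 0% |
| 0.2 | −0.3 | 0.2 × 0.3 × 3.64 = 0.218 | 7% |
| 0.2 | −0.5 | 0.2 × 0.5 × 3.64 = 0.364 | 12% |
| 0.5 | −0.3 | 0.5 × 0.3 × 3.64 = 0.546 | 18% |
| 0.5 | −0.5 | 0.5 × 0.5 × 3.64 = 0.910 | 30% |

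The bias is upward if fortification raises the covariate and downward if it lowers it.

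**4. Consequence for the test.** Simulation with 25 per group and 40,000 trials per case:

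| T | a | r | ANCOVA estimate | ANCOVA rejects | t-test rejects |
|---|---|---|---|---|---|
| 3.0 | −0.5 | −0.5 | about 2.1 | 59% | 81% |
| 3.0 | 0 | −0.5 | 3.0 | 90% | 81% |
| 3.0 | +0.5 | −0.5 | 3.9 | 98% | 81% |
| 0 | 0 | −0.5 | 0 | 5% | 5% |
| 0 | ±0.5 | −0.3 | ±0.55 | 8% | 5% |
| 0 | ±0.5 | −0.5 | ±0.91 | 16% | 5% |

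Check by hand for |a| = 0.5, r = −0.5. The residual SD is 3.64 × √0.75 = 3.152, and the standard error is about 3.152 × √(2/25) × √(1 + 0.5²/4) = 0.919. With T = 3.0 and a = −0.5, 2.09/0.919 = 2.27; less the critical value of about 2.01 this leaves 0.26, so power is about 60%. With T = 0, 0.91/0.919 = 0.99, and 0.99 − 2.01 = −1.02 gives rejection of about 15% to 16%. Both agree with the simulation.

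**5. Shared cause.** A separate large-sample simulation assumed a true total effect of 3.0 and a loss of 0.5 g/kg/day per interruption. If fortification adds one interruption per infant, the unadjusted estimate stays at 3.0 and the adjusted one is 3.5, or 3.8 with an unmeasured common cause. If it removes one, the adjusted estimate is 2.5, or 2.2 with the common cause. If it changes nothing, both are 3.0.

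**The case against.** The strongest reply is that an unbiased analysis is already planned: the t-test estimates the total effect and the trial is sized on it. The phrase "analysis of covariance (ANCOVA) will be used with the main effect of interest being the group effect" names the term of interest within the model; it does not rank the ANCOVA above the t-test. That reading is fair, and the point does not depend on the other one. It remains that the t-test is described as preliminary, the ANCOVA follows it, and neither is designated primary. A separate analysis plan might settle the order, but the covariate list is already fixed here.

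Second, section 2 reports that no study has shown fortifiers to affect NEC or tolerance, and section 8 expects no unique risks in either group. No passage says that fortification changes acidosis. This is why the point is conditional. But section 12a still lists intolerance and NEC as foreseeable risks, and a link not yet demonstrated is not a link excluded.

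Third, section 11a withdraws infants with NEC stage IIb or higher, so NEC may vary little among infants with 28-day data. That limits the part NEC plays but leaves feed interruptions untouched, and that covariate alone sustains the point.

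Fourth, the shift and correlation are assumed, and the model uses one continuous covariate although NEC and acidosis would naturally be yes/no. The figures are therefore illustrative. It is also true that with no shift the adjustment gains power (90% against 81% at r = −0.5). Baseline covariates can offer a gain in precision without the risk.

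Finally, section 9a already compares these variables by group, partly to examine differences and partly to look for confounding. That comparison would reveal a shift but would not correct the adjusted estimate.

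**Conclusion.** The concern holds in its conditional form. Three of the four covariates named for the ANCOVA are wholly or partly post-randomisation, and the protocol treats them as outcomes or links them to risks of the intervention. If fortification shifts any of them and they are related to growth, the adjusted group effect is not the total effect the trial asks about. Under the assumed shifts of 0.2 to 0.5 SD and correlations of −0.3 to −0.5, the bias is 0.2 to 0.9 g/kg/day in either direction. At the edge of that range, power falls to about 59% or the false-positive rate rises to about 16%. With no shift there is no bias. The sample size and the t-test stand. Because the flaw lies in an analysis of the primary outcome and no rule says which result governs, it should be corrected before the data are analysed.

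**What to change.** In section 9a:

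1. Remove feed interruptions, metabolic acidosis and NEC from the ANCOVA. Keep gestational age and, if wanted, birth weight and sex.
2. Name one primary analysis of 28-day weight growth velocity. The baseline-adjusted ANCOVA is preferable, with the unadjusted t-test as supportive. Making the t-test primary would also be valid and would match the sample size calculation directly.
3. Present the group comparisons of interruptions, acidosis and NEC as outcome comparisons, not as a search for confounders.
4. Label any model that adjusts for these three as exploratory, and state that it does not estimate the total effect.

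The cost is a wording change to the protocol. Gestational age, birth weight and sex are already collected, and neither the sample size nor the data collection changes.

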Protocol Title: Early Fortification of Human Milk for Very Low Birth Weight Infants and Effects on Growth Velocity

Principal Investigator: [name], DO

1. Objectives

Describe the purpose, specific aims, and hypothesis:

The purpose of this investigation is to determine whether early fortification of human milk feeds improve growth outcomes for very low birth weight infants (VLBW) (birth weight 1000-1500 grams). We hypothesize that introducing higher caloric feeds at the onset of enteral feeds will improve early growth metrics in VLBW infants as compared to infants who begin human milk fortification after the first week of life, which represents our present standard of care. The primary outcome for this study is growth velocity (g/kg/day) at 28 days of life.

2. Background

Describe the background and rationale for the study:

Human milk, maternal or donor milk, is the standard of care for feeding premature infants. However, human milk alone does not provide sufficient energy, protein, fat, and micronutrients to meet the demands of the VLBW premature infant. Thus, slow growth can persist for preterm infants and catch-up growth can be incomplete even after discharge from the NICU, and slow extra-uterine growth (weight, length, and head circumference) is associated with poor neurodevelopment and lower intelligence in school age children born preterm. Using human milk fortifiers (HMF) increase nutrient density of human milk and allows for infants to maintain a human milk-based diet, which has been shown to reduce the incidence of necrotizing enterocolitis (NEC) and improve cognitive outcomes in preterm infants.

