A sample size of 25 per group, for a total of 50 subjects will be needed.

5. Recruitment Methods

Describe when, where, and how potential subjects will be recruited:

All neonates admitted to the NICU who have a birth weight of 1000-1500 grams will be eligible for this study. Screening will include chart review to ensure inclusion criteria is met. Parents (legal guardians) of eligible neonates will be approached for study participation by the PI or co-Investigators.

6. Multiple Site	 N/A
7. Reliance Agreements/Single IRB	 N/A

8. Procedures Involved

a. Describe the procedures involved to include those procedures that are standard evaluation and/or care and those that are solely for research purposes:

Feeding Protocol

All VLBW infants in AU's NICU are provided a standard feeding protocol that has been in use since 2011 and includes fortification of human milk with Enfamil High Protein Liquid Human Milk Fortifier (HP HMF) on feeding day 8. Study participants will be randomly assigned to receive standard of care (ie fortification on feeding day 8) or fortification on feeding day 1. In general, feedings for preterm infants are started in the first 48 hours.

b. Describe and explain the study design:

If the study involves multiple conditions where each condition involves different procedures, please provide a table that breaks down the procedures by condition and in chronological order. Include when and where they are performed.

1. Subjects will be randomly assigned to one of two groups using blocked randomization to ensure equal allocation throughout enrollment. Blocks of size 4 and 6 will be randomly determined and then the group assignment will be randomly permuted within each block. Initiation of enteral feedings, enteral volume advancement, and weaning off parental nutrition will follow the standardized NICU feeding protocol.
2. Subjects will be fed a diet of human milk per standard NICU feeding protocol. Should maternal milk supply be inadequate to meet daily volume needs, donor milk will be used per standard NICU feeding protocol. Importantly, mothers (or guardians) must provide written consent for donor human milk. This consent is separate from the study consent and will be required for study participation.
3. Enfamil High Protein Liquid Human Milk Fortifier (HP HMF) will be used to fortify maternal milk.

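### The adjusted analysis of 28-day growth velocity does not pre-specify birth weight as a covariate; this is a minor loss of precision and pre-specification, not a bias

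*Protocol*

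**What the plan says.** - **Outcome.** Protocol section 1: "The primary outcome for this study is growth velocity (g/kg/day) at 28 days of life". The Weight Gain part of section 8 defines velocity as 1000 × (Wn − W1), divided by the number of days times the mean of Wn and W1.
- **Starting weight.** W1 is described only loosely ("1 = interval of time chosen"). The weighing schedule reads "Body weight will be measured within 24 hours of birth and then every 7 days until 28 days of life", so for velocity at 28 days W1 is most naturally the birth weight. That is an inference, not a stated definition.
- **Range and allocation.** Section 3 admits birth weights of 1000-1500 g. Section 8.b: "Subjects will be randomly assigned to one of two groups using blocked randomization to ensure equal allocation throughout enrollment". Blocks are of size 4 and 6, and no stratification by birth weight is stated.
- **Analysis.** Section 9.a starts with a t-test, described as preliminary, and then an ANCOVA: "Covariates that will be adjusted for include gestational age, total number of feed interruptions, incidence of metabolic acidosis, and NEC". The same section compares all collected record data and anthropometric measures between arms to look for confounding, but gives no rule by which a variable so screened enters the model.
- **Size.** Section 9.b: "The sample size was determined assuming an alpha level of 0.05, power of 80%, a common standard deviation of 3.64, and a two-sided two-sample t-test", and "A sample size of 25 per group, for a total of 50 subjects will be needed".

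**The concern.** Of the four named covariates, only gestational age is fixed before treatment. Birth weight is also fixed before treatment, is recorded for every infant because it decides eligibility, and appears in both the numerator and the denominator of the outcome. Gestational age is a partial substitute at best: within a fixed birth-weight band, maturity and size are different information.

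Two things are at stake. The first is precision, which is scarce because the trial is sized on the largest of three assumed effects. The second is pre-specification. If the arms differ visibly in birth weight, the plan as written does not say whether the model will adjust for it, so the choice would be made with the results in view.

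**Working it through.** **1. The plan's own figure.** Inputs from section 9.b: SD 3.64, two-sided alpha 0.05, power 80%, means 10.56 and 13.56 (difference 3.0). The two-sample t-test with the noncentral t distribution gives 25 per group, with power 81.5%. The other two rows, 74 and 53, also reproduce exactly. The standard error of the group difference is 3.64 × √(2/25) = 1.03 g/kg/day.

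**2. Size of a chance imbalance.** The Protocol gives no birth-weight SD. Uniform on 1000-1500 g (assumed), it is 500/√12 = 144.3 g. The standard error of the difference in arm means is 144.3 × √(2/25) = 40.8 g. For a 50 g gap, z = 50/40.8 = 1.23, so a gap of at least 50 g in either direction has 22% probability. For an assumed SD of 100 to 150 g, the standard error is 28 to 42 g and that probability is 8% to 24%.

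**3. Effect on velocity.** Take a mean birth weight of 1250 g (assumed) and 10.56 g/kg/day. Solving the formula over 28 days gives a gain of 433.7 g, or 15.49 g/day. With a constant absolute gain, velocity = 1000 × 433.7 / [28 × (W1 + 216.9)].

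- At W1 = 1275 g: 10.38.
- At W1 = 1225 g: 10.74.
- Shift for a 50 g gap: 0.36 g/kg/day, which is 0.36/1.03 = 0.35 of a standard error and 0.36/3.0 = 12% of the planned difference.
- At the 95% limits of chance imbalance (55 to 83 g for SD 100 to 150 g): 0.40 to 0.60 g/kg/day.

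If gain is proportional to weight, Wn = k × W1, W1 cancels from the formula and the shift is exactly zero.

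**4. Validity.** In 20,000 simulated trials with no treatment effect, uniform birth weights and an assumed correlation of −0.3 between birth weight and velocity, the type I error was 4.9% without birth weight in the model and 5.0% with it. Both estimates were centred on zero. The empirical standard error fell from 1.03 to 0.99.

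**5. Power.** With birth weight as the only covariate, residual SD = 3.64 × √(1 − ρ²) on 47 degrees of freedom and a true difference of 3.0:

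| ρ (assumed) | 0 | 0.2 | 0.3 | 0.4 |
|---|---|---|---|---|
| Power | 81.4% | 83.0% | 84.9% | 87.6% |

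Under constant absolute gain, the slope of about 0.72 per 100 g implies ρ of about 0.72 × 1.443 / 3.64 = 0.29 in absolute value. This calculation charges the degree of freedom but not the small variance inflation from chance covariate imbalance, and it gives gestational age no share, so it is favourable to the change.

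The more relevant comparison adds birth weight to a model that already holds group and gestational age. It was simulated with 8,000 trials and an assumed correlation of 0.5 between the two covariates:

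| Gain model (assumed) | Without birth weight | With birth weight |
|---|---|---|
| Constant in g/day | 81.3% | 83.3% |
| Proportional to square root of weight | 80.4% | 80.1% |
| Proportional to weight | 81.0% | 80.2% |

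A repeat of this check gave about +1 to +2 points, no change, and about −1 point respectively.

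**The case against.** The case for leaving the plan alone is substantial, and most of it stands.

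- **The formula already scales for size.** It divides by mean weight, and the feeding tables in section 8 set intake per kilogram in both arms. That leans towards gain rising with weight, where adjustment helps little or costs a fraction of a point. It does not establish proportional growth, and the Protocol gives no figure on it.
- **A reader might infer that a chance imbalance passes directly into the primary result.** The documents do not support that. Imbalance arising under randomisation is already part of the outcome SD and of the test's standard error, and the simulated type I error is unaffected.
- **A reader might also compare individual infants.** At 15.49 g/day the formula gives 12.7 at 1000 g and 9.0 at 1500 g, a span of 3.7 that looks large beside the 3.0 used for sizing. The comparison misleads: it sets two infants at the eligibility limits against a difference between arm means. The like-for-like figure is 0.36 against 1.03.
- **The simulated model is simpler than the planned one.** The planned ANCOVA also contains feed interruptions, metabolic acidosis and NEC. The power figures are therefore indicative only.
- **The list is open, and a SAP may complete it.** The covariates are introduced as a list that may not be exhaustive, and anthropometric measures are screened. This part stands only in part: section 9.a already names the adjustment set, and the screening sentence has no entry rule. Read as permission to add variables, it makes adjustment for birth weight a data-driven choice.

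**Conclusion.** The point holds as a minor one. The primary outcome's ANCOVA names one baseline covariate and omits another that is in hand before treatment and most naturally enters the outcome formula. Nothing in the planned comparison is biased or invalid as a result.

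For a 50 g imbalance the size is between zero (gain proportional to weight) and about 0.36 g/kg/day (constant absolute gain), roughly a third of a standard error, before gestational age takes up any of it. The effect of adding birth weight on power runs from about +2 points to about −1 point. These figures rest on an assumed birth-weight distribution, a mean of 1250 g, a correlation of 0.5 with gestational age and a range of gain models, none of which the Protocol gives. The argument for acting is therefore mainly pre-specification, with a modest possible gain in precision.

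**What to change.** In section 9.a, name birth weight (continuous, the W1 of the velocity formula) beside gestational age as a pre-specified baseline covariate in the ANCOVA of 28-day weight growth velocity. State in the Weight Gain part of section 8 that W1 for this outcome is the birth weight, if that is what is meant.

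The cost is one added term, one degree of freedom, no new data, and about 1 power point or less if birth weight carries no information. The sample size need not change. Three of the four covariates now named are recorded after feeding begins; that is a separate question, which this change does not settle.
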